### c.1.e Photosensitizer protocol

After diagnosis and entry criteria are confirmed, patients will receive intravenous verteporfin 0.4 mg/kg bodyweight, 60 minutes before laser activation. The drug-light interval will be recorded to the nearest minute in the case report forms, with an acceptable treatment window being 60-90 minutes. This allows for the re-positioning of the fiber if multiple sites are to be treated. Patients will remain in subdued lighting on the ward for 24 hours after injection, followed by re-adaptation to indirect sunlight for increasing periods during the morning and late afternoon of the next day. Bright indoor light will be permitted after 24 hours and exposure to direct sunlight allowed after 48 hours.

### c.1.f EUS-guided PDT Light Treatment

All laser procedures will be carried out in accordance with the local laser safety rules as specified by the hospital laser protection advisor. When the EUS needle has been confirmed to be correctly sited in the tumor under real-time EUS control, a diffuser fiber of appropriate length will be passed down to the tip of

the needle. Prior to use, the system will be calibrated to deliver 150 mW/cm along the length of each diffuser fiber, with the light dose delivered kept constant at 40 -80 J/cm. The illumination time is expected to be approximately 5 minutes based upon the linear irradiance and the target dose. After delivery of the planned light dose at each site, the needle and fiber will be removed.

#### **c.1.g Dosimetry Studies: PS fluorescence and CT Perfusion**

Two levels of dosimetry will be completed in this patient group. Initially we will complete PS dosimetry by placement of a bare tip fiber down the EUS guided needle, immediately prior to the treatment fiber placement. Fluorescence measurements will be completed with the Dartmouth Dosimeter system, measurements being taken at several points across the lesion. Data from the phase 1 trial was inconclusive about the value of this approach, because of high variability in placement, through the percutaneous needles used. The EUS needle placement is likely to be more convenient for sampling at more sites and to assess repeatability of multiple placements of the fiber, although patients will only have one EUS examination when they are photosensitised. We will also study the correlation between the PS fluorescence level seen and the perfusion (as measured by CT contrast) observed at the fiber location.

In the phase 1 trial, a strong correlation was seen between the volume of necrosis normalized by the light dose delivered, and CT contrast enhancement seen. We need to confirm this observation in the phase 2 trial when all subjects are receiving the same light dose. Thus, pre-treatment CT scans ± contrast will be acquired and used for all subjects recruited into this trial. Following analysis of these data, if the strong correlation is confirmed, we will then be able to recommend adjusting light delivery to modulate the anticipated volume of necrosis in future patient studies. Additionally, Project 4 is analysing this in the rabbit pancreas tumor model.

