### **Hypothesis 1: EUS-guided PDT will provide effective ablation of solid lesions of the pancreas (multi-center phase II clinical trial at UCL + Mayo).**

Clinical use of PDT for PanCa has been pioneered by the Project 2 group, and a positive correlation was established between delivered energy and the extent of tumor necrosis around interstitial fibers, with no serious adverse events. We aim to improve the approach by moving to a minimally invasive approach of EUS, in conjunction with dosimetry to monitor treatment (jointly with *Project 4*).

**Aim 1.** To participate in the conduct a phase II study of EUS-guided PDT in PanCa. PDT will be done initially at a single site with a fixed light dose for the first group of patients, then at multiple sites to match the zone of tumor necrosis to tumor volume.

This work will lead into the next logical step in the trial, which was the major goal of Project 2, namely a combination therapy trial using PDT, standard chemotherapy and in patients with advanced or locally advanced and metastatic disease. The advanced cancer patients will be defined as patients with at least a 50% increase in tumor volume or new metastasis regardless of whether the patients had chemotherapy. All participants will be within ECOG performance status of 0-2. This work provides a direct bench-to-bedside translation, as we will use the most effective combination sequence form project 3 as they study in pre-clinical work. While this is not the goal of this current supplement, it is a future direction, which will be expedited by the completion of this proposed Phase II trial.

After intravenous administration of verteporfin, fluorescence readings will be taken from the patient's buccal mucosa to register the fluorescence peak. This is performed using a mobile fluorimeter that uses an ipad as the processor. The device delivers a very small amount of light to the buccal mucosal and can measure nanogram levels of drugs. A gradient spectrophotometer is coupled to a CCD to record the fluorescence. Background fluorescence will be performed earlier in the day from the same area of buccal mucosa. The measurements will be taken every 10 minutes until the procedure (total 6-9 measurements).

We plan to take FNA biopsies of the lymphocytes to assess immune response due to treatment.

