#### **b.1 EUS-guided PDT will enable effective ablation of solid tumors of the pancreas.**

Based on our collaborators at the University College London's previous animal experimental work, and our pre-clinical and clinical trials of pancreatic PDT, a phase I study of verteporfin PDT in locally advanced unresectable PanCa (VERTPAC-01) was undertaken. In the initial dose escalation part of the study, patients were treated with verteporfin PDT to assess its general safety profile, to determine the optimum treatment parameters needed to achieve effective and safe necrosis of tumor, and to confirm safety of administration of subsequent conventional palliative chemotherapy. Inclusion criteria included a histopathological/cytological diagnosis of PanCa, unresectable, non-metastatic disease confirmed at multidisciplinary review and adequate biliary drainage (serum bilirubin < 2.5 x upper limit of normal). All patients received a dose of verteporfin 0.4 mg/kg bodyweight intravenously, followed by light activation 60 minutes later under subdued lighting conditions. Treatment was via a single 10 mm tip diffuser fiber which was placed under CT guidance by an experienced radiologist (Figure 1). With increasing light doses, there was an increase in the extent of tumor necrosis around the fiber with no serious adverse events or reports of photosensitivity. This study aims to replicate these findings using the minimally invasive approach of EUS. Initially, only a single position of the laser fiber will be used, but in later patients multiple fiber positions will be used to show that it is possible to treat the full volume of appropriate cancers with endoscopic placement of the treatment fiber in more than one site. This is essential to show that endoscopic fiber placement can cover a comparable volume of tumor to the multi-fiber, percutaneous approach used in the previous studies.

**Fig. 2. Patient undergoing verteporfin PDT.** The image on the left shows a baseline contrast-enhanced CT with a low attenuation mass in the head of the pancreas. The centre image shows percutaneous needle placement into the tumour. The image on the right shows the day 5 post PDT contrast-enhanced CT with a  $2.67 \text{ cm}^3$  zone of necrosis in the region of the pancreatic head.

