#### c.1.b Design of VERTPAC-02 study

This will be a phase II study of 15 (UCL) + 15 (Mayo) patients with histologically proven advanced or locally advanced PanCa or other solid tumors unsuitable for surgical resection. In the first 5+5 patients, EUS guided verteporfin PDT will be used with light delivered at just one site. In the following 10+10 patients, light will be delivered with the fiber at multiple positions, as required to ensure treatment of all appropriate areas of the cancer, as was done in the previous studies with percutaneous fiber insertion. Each patient will be given verteporfin 0.4 mg/kg bodyweight intravenously, followed by light activation 60 minutes after photosensitization (acceptable treatment window 60- 90 minutes). Light delivery will take place via a 5-20 mm length diffuser fiber placed under EUS guidance using red laser light at 690nm. The light dose delivered down the fiber will be fixed at 40 -80 J/cm, which was found to be optimum in our previous VERTPAC-01 study. All patients will be prescribed ciprofloxacin as a prophylactic to reduce the potential risk of infection associated with the fine needle puncture of the tumor. If a patient is allergic to ciprofloxacin, another acceptable broad spectrum antibiotic will be prescribed at the investigators discretion.

Patients will be evaluated by contrast enhanced CT at 2 days after PDT (treatment day 3), and they will be able to commence conventional palliative chemotherapy after that if they so wish within a week of PDT. Patients will also have additional blood draws taken for biomarker analysis before, during, and after their treatment. In previous studies, it was a protocol requirement that chemotherapy

not be given within a month of PDT. However, PDT is a local, one off treatment and chemotherapy is systemic and ongoing. It is an important innovation to give chemotherapy much earlier after PDT as our previous study on PDT for biliary tract cancer showed that delay in giving chemotherapy after PDT put patients at a disadvantage. Treatment response and time to disease progression will be assessed by CT scans at three-monthly intervals, as part of usual practice. Thereafter, patients will continue to be followed up for survival data. Second line chemotherapy and/or re-treatment with verteporfin PDT for progressive disease will be at the discretion of the investigators.

**c.1.c Patient eligibility:** See Table 1.

Inclusion Criteria	Exclusion Criteria

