##### **SECONDARY Response evaluation**

- Progression-free survival will be determined at 6 months follow-up and beyond.
- CEA and/or CA19.9 4-weekly if elevated prior to therapy
- ECOG performance status and Brief Pain Inventory pain scores, prior to therapy and at follow-ups
- Comparison will be made between the documented extent of necrosis and both the measured photosensitizer concentration, as assessed by fluorescence, and the estimated necrosis volume based on CT with and without contrast.

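### The light dose called constant is a 40–80 J/cm range with no selection rule, the stated 5 minutes fits only about 40–50 J/cm, and the photosensitizer–necrosis comparison names no energy term

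*Combined protocol and SAP*

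**What the plan says.** **Dose.** Section c.1.b: "The light dose delivered down the fiber will be fixed at 40 -80 J/cm". Section c.1.f, after setting the calibration at 150 mW/cm along each diffuser, continues: "with the light dose delivered kept constant at 40 -80 J/cm".

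**Time.** Section c.1.f: "The illumination time is expected to be approximately 5 minutes based upon the linear irradiance and the target dose".

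**Delivery.** Section c.1.b: "Light delivery will take place via a 5-20 mm length diffuser fiber". The first 5+5 patients are treated at one position and the next 10+10 at as many as the tumor requires.

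**Premise of the dosimetry work.** Section c.1.g reports that in phase 1 the necrosis volume, normalized by light dose, correlated strongly with CT enhancement. It then says: "We need to confirm this observation in the phase 2 trial when all subjects are receiving the same light dose". It leaves adjustment of light delivery to later studies.

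**Planned comparison.** Under SECONDARY Response evaluation (c.1.h): "Comparison will be made between the documented extent of necrosis and both the measured photosensitizer concentration". The same bullet adds the necrosis volume estimated from CT. It mentions neither light dose nor energy.

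**Energy and necrosis.** Hypothesis 1 says that "a positive correlation was established between delivered energy and the extent of tumor necrosis around interstitial fibers". Section b.1 says of phase 1: "With increasing light doses, there was an increase in the extent of tumor necrosis around the fiber".

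**The concern.** A dose cannot be both constant and anywhere in a twofold range. With no rule, the two centers could work at opposite ends of 40–80 J/cm and both comply, and the premise in c.1.g would then be untrue. An operator who goes by the expected time when a higher dose was meant would deliver less light than planned.

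The second part concerns the analysis. By the protocol's own account, necrosis depends on delivered energy. Energy will differ between patients, so a comparison of necrosis with photosensitizer level that ignores it carries extra scatter, which weakens any true relation. Phase 1 left the fluorescence measure inconclusive because needle placement varied (c.1.g). EUS placement is meant to improve on that, and scatter that one model term can remove should not be left in.

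**Working it through.** **Inputs.** Linear irradiance 0.150 W/cm, dose 40–80 J/cm and time about 5 min (c.1.f); diffuser length 0.5–2 cm and the split by number of positions (c.1.b); single 10 mm diffuser in phase 1 (b.1).

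**1. The stated time.** Time = dose ÷ irradiance.

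| Dose (J/cm) | Calculation | Time |
|---|---|---|
| 40 | 40 ÷ 0.150 = 267 s | 4.4 min |
| 45 | 45 ÷ 0.150 = 300 s | 5.0 min |
| 50 | 50 ÷ 0.150 = 333 s | 5.6 min |
| 60 | 60 ÷ 0.150 = 400 s | 6.7 min |
| 80 | 80 ÷ 0.150 = 533 s | 8.9 min |

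The plan's 5 minutes is reproduced at 45 J/cm, not across the range. Allowing for rounding, 4.5 min gives 4.5 × 60 × 0.150 = 40.5 J/cm and 5.5 min gives 49.5 J/cm. The time thus agrees with about 40–50 J/cm. Five minutes delivers 45 ÷ 80 = 56% of the upper end. The upper end takes 533 ÷ 300 = 1.78 times as long as stated. Reaching 80 J/cm in 5 min would need 80 ÷ 300 = 0.267 W/cm, not the 0.150 W/cm calibrated.

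**2. Energy at constant dose.** Energy per position = J/cm × length in cm. At 45 J/cm this is 45 × 0.5 = 22.5 J to 45 × 2 = 90 J, a fourfold range from diffuser length alone. Total energy is the sum over positions: one position in 5 + 5 = 10 patients, several in 10 + 10 = 20. The number of positions is not stated, nor is how often each length will be used.

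**3. The CT normalizer.** Joules ÷ (J/cm) = length in cm. With the single 10 mm diffuser of phase 1 this is 1.0, so the two normalizers were numerically equal. With 5–20 mm it is 0.5 to 2.0 per position, so the choice now changes the result.

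**4. Where energy enters the analysis.** The secondary objective in c.1.a treats necrosis as a function of delivered energy, using pre-treatment CT. Section c.1.g normalizes the phase 1 necrosis volume by dose. Both concern CT. No section links energy to the photosensitizer comparison.

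**5. Illustration of direction only.** None of these assumptions is in the documents: log necrosis = log photosensitizer + log energy + noise (SD 0.3); photosensitizer CV 30% or 50%; dose uniform over 40–80 J/cm and independent of photosensitizer; one position per patient. The correlation of log photosensitizer with log necrosis was simulated.

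| Setting | CV 30% | CV 50% |
|---|---|---|
| One constant dose and length | 0.699 | 0.845 |
| Dose 40–80 J/cm, one length | 0.632 | 0.797 |
| Dose 40–80 J/cm, lengths 5, 10, 20 mm equally likely | 0.402 | 0.577 |

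Dividing necrosis by energy brings all settings back to about 0.70 and 0.84–0.85. Under these assumptions the dose range alone costs little and varying length costs more.

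**The case against.** **Dose selection is not wholly ignored.** The project summary promises CT-based, patient-specific treatment, and item 2 of the Innovation section describes contrast CT for optimizing light dose. Aim 1 applies a fixed dose to the first group. Section c.1.f refers to a planned dose at each site, and the registration text says the regimen is defined on entry. These show that planning was intended, but none is a rule. They also pull against c.1.g, which puts adjusted delivery in future studies. The omission stands.

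**The time is only approximate.** This is fair. A reader might infer that only 45 J/cm is compatible with it, but 4.4 minutes at 40 J/cm can reasonably be called about 5. The stated time excludes the upper part of the range, not everything except 45.

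**Joules are not the protocol's dose.** Also fair. Combining the extremes of dose and length gives 40 × 0.5 = 20 J to 80 × 2 = 160 J per position, and a reader might set that eightfold spread against the same-dose sentence. The protocol defines dose per cm, so only the twofold range bears on that sentence. Diffuser length and number of positions follow the tumor and are not faults. They matter for the analysis only.

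**Silence is not exclusion.** The c.1.h bullet is a summary that specifies no model, and an energy adjustment may have been intended. It should then be stated, as energy is for the CT work.

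**Conclusion.** The concern holds at moderate weight. As written, the plan does not ensure that all subjects receive the same light dose. The range is twofold, it has no selection rule, and the stated time agrees only with about 40–50 J/cm. This rests on the protocol's own dose, irradiance and time. Separately, the photosensitizer comparison should account for delivered energy, because the protocol itself says necrosis rises with energy or light dose and because energy varies even at constant J/cm.

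Three stronger conclusions are not supported:

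- **Primary response.** A reader might infer that it is weakened, since the sample size section ties the 12 mm criterion to these treatment parameters. But c.1.b calls the whole 40–80 J/cm range optimum, and nothing gives response by dose.
- **Confounding.** This would need energy to be related to photosensitizer level, which the documents do not show. Dilution is the expected effect, and its size cannot be calculated from the documents.
- **CT analysis lacking an energy term.** It has one. Its gaps are the unnamed normalizer and the possibility, left open by the project summary and the Innovation section, that dose is chosen from the same CT enhancement that is tested as the predictor. Bias could then go in either direction.

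**What to change.** 1. State one J/cm value; 45 agrees with the stated time, though the choice is the sponsor's. Or keep 40–80 J/cm with a written selection rule that says whether CT enhancement may inform the choice. Give the matching time: 4.4–8.9 min for the full range.
2. Unless one dose is set, correct the same-dose sentence in c.1.g.
3. Record J/cm, diffuser length, illumination time and joules for each position on the case report form.
4. In the photosensitizer comparison, adjust for delivered energy, with the patient as the unit: total necrosis, total joules and mean fluorescence. For example, regress log necrosis on log energy plus photosensitizer level, which does not require necrosis to be proportional to energy. If any patient has zero necrosis, use a rank partial correlation given energy. This is needed even with one J/cm value, because length and positions still vary.
5. For the CT analysis, say whether J/cm or total joules is the normalizer, and do not choose dose from the CT enhancement under test.

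The cost is text changes, a few form fields and one model term, with no added patients or visits. The laser safety section already requires a stop watch and a power meter, and study data already go on case report forms.

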#### **c.1.h Treatment Evaluation**

##### **PRIMARY Response evaluation**

- Contrast-enhanced CT scans of the pancreas will be evaluated before treatment and on day 3 (after treatment on day 1), for measurement of tumor volume using RECIST criteria and to assess the extent of tumor necrosis after treatment.

##### **SECONDARY Response evaluation**

- Progression-free survival will be determined at 6 months follow-up and beyond.
- CEA and/or CA19.9 4-weekly if elevated prior to therapy
- ECOG performance status and Brief Pain Inventory pain scores, prior to therapy and at follow-ups
- Comparison will be made between the documented extent of necrosis and both the measured photosensitizer concentration, as assessed by fluorescence, and the estimated necrosis volume based on CT with and without contrast.

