#### a.1: Pancreatic Cancer

Worldwide, PanCa is one of the top 10 leading causes of cancer deaths, and ranks fourth as a cause of cancer death in the UK and USA (1). Overall, the long term prognosis of the disease is poor with a one-year survival rate of no more than 10%. For cancers staged more advanced than Stage 1B, 5 year survival is less than 7%. For non-metastatic disease, median survival is 6–10 months although for those with metastatic disease at presentation, survival is only 3–6 months (2, 3). While there have been small gains in therapeutic options for patients in recent years, there has been no significant improvement in overall outcome for more than two decades. Novel treatment strategies for advanced tumors and improved detection and ablation of premalignant lesions are necessary to improve outcome.

According to the SEER (Surveillance, Epidemiology, and End Results Program) database, it is projected that there will be 48,760 new cases of pancreatic cancers in the United States (incidence of 10.4/100,000) with a five year projected survival rate of only 7.2%. The lifetime risk of developing pancreatic cancer is 1.5% in both men and women. There is also estimated to be 40,560 deaths due to pancreatic cancers in 2015. There has not been a major advancement in survival with unresectable pancreatic cancer that is the primary rationale for the development of new innovative therapies such as photodynamic therapy.

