### c.1.d Pre and post procedure assessments:

See Table 2.

TABLE 2. Pre- and Post-Procedure Assessments for the VERTPAC-02 Study

Timepoint	Assessment
Pre-procedure	
 
Informed consent
 
Symptom and adverse event monitoring
 
Physical examination (including weight and ECOG performance status)
 
FBC, INR and biochemical profile including tumor markers (CEA/CA19-9), amylase, glucose
 
Pancreatic protocol CT chest, abdomen & pelvis (day -28 to 0)
 
Copy of report of prior histological or cytological proof of PanCa
 
QOL forms (EORTC QLQ30)
 

Post procedure	
 
Following treatment, patients will be monitored closely on the ward. The following protocol will be used to assess patients post treatment
 

Day 2 and 3 after the treatment on Day 1	
 
Symptom and adverse event monitoring, physical examination (including ECOG performance status)
 
FBC and biochemical profile including amylase, glucose
 
Pancreatic protocol CT on day 3, prior to planned discharge
 

Day 14	
 
Symptom and adverse event monitoring, physical examination (including ECOG status)
 
FBC and biochemical profile including amylase, glucose
 
QOL forms (EORTC QLQ30)
 

Months 3, 6 and 12:	
 
Symptom and adverse event monitoring; physical examination (including weight and ECOG status)
 
FBC and biochemical profile including CEA/CA19-9
 
Pancreatic protocol CT
 

Clinical and laboratory assessments will be repeated prior to discharge (anticipated at day 3). All patients will be followed up on day 14 then at three, six and 12 months. At each visit, clinical symptoms will be reviewed, and quality of life and laboratory assessments repeated. In patients in good general condition with evidence of residual tumor or local tumor progression on repeat CT, up to two further PDT treatments may be offered at a minimum of four week intervals. If patients are unable to return for follow up they will be contacted by phone to complete the QOL assessment, as well as asked if they have had adverse events, hospitalization related to disease or progression of disease.

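### ECOG and pain scores are secondary measures at follow-up, but patients too ill to attend have no planned score and Table 2 schedules the pain scale at no visit

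*Combined protocol and SAP*

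**What the plan says.** The SECONDARY Response evaluation list in section c.1.h includes "ECOG performance status and Brief Pain Inventory pain scores, prior to therapy and at follow-ups". It gives no summary statistic, denominator, principal time point, or rule for deaths and missed visits.

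The visit schedule is in section c.1.d: "All patients will be followed up on day 14 then at three, six and 12 months". In Table 2, ECOG is always part of the clinic examination; at months 3, 6 and 12 the entry is "physical examination (including weight and ECOG status". BPI appears nowhere in Table 2, not even before treatment. The patient-reported instrument listed there is a different one: "QOL forms (EORTC QLQ30".

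For non-attenders, the same section says "If patients are unable to return for follow up they will be contacted by phone to complete the QOL assessment". The call also asks about adverse events, disease-related hospitalization and progression. It mentions neither ECOG nor BPI.

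Two other provisions are relevant. Section c.1.b follows patients for survival, and *Withdrawal of Patients* (section 6.1.1) continues data collection after withdrawal from treatment. Neither is tied to these two scales.

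On prognosis, section a.1 gives a median of 6 to 10 months for non-metastatic disease. For metastatic disease at presentation it says "survival is only 3–6 months".

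**The concern.** Two routes leave a patient without a score at a planned visit. One is death, which is common in this disease within the follow-up window. The other is being alive but too ill to travel: the phone contact exists for these patients but omits both scales.

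Both routes probably remove the patients with the poorest function and most pain. Whatever is then summarized at months 3, 6 and 12 describes a selected group. The trial has one arm ("This will be a phase II study of 15 (UCL) + 15 (Mayo) patients"), so no control group with similar attrition is available to show how much of an apparent change is selection. At stake is a misleading statement about function or pain after treatment. For BPI there is a further risk that no systematic data exist at all.

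**Working it through.** The plan states no missing-data rate for ECOG or BPI, so there is no figure of its own to reproduce. The check has three parts.

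**1. What is collected, and from whom**

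| Patient status at a follow-up visit | ECOG | BPI | Quality of life |
|---|---|---|---|
| Attends clinic | yes (examination) | not scheduled | section c.1.d text: yes |
| Alive, cannot return | not in phone contact | not in phone contact | yes (phone) |
| Dead | no rule | no rule | no rule |

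**2. How many could be dead**

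Inputs: n = 30 (c.1.b); medians of 3, 6 and 10 months, spanning the figures in a.1 (the metastatic figure is read as a median). Exponential survival is my assumption. Proportion dead by month t = 1 − 0.5^(t/median).

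| Median | Month 3 | Month 6 | Month 12 |
|---|---|---|---|
| 10 months | 19% (5.6 of 30) | 34% (10.2) | 56% (16.9) |
| 6 months | 29% (8.8) | 50% (15.0) | 75% (22.5) |
| 3 months | 50% (15.0) | 75% (22.5) | 94% (28.1) |

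Cross-check: a.1 also describes the disease overall "with a one-year survival rate of no more than 10" per cent. With exponential survival, 10% alive at month 12 means √0.10 = 0.316 alive at month 6, so 68% dead. This lies inside the range.

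Case mix at month 6: 34% to 50% dead if all are non-metastatic, and 50% to 75% if all are metastatic. A half-and-half cohort gives (34 + 50)/2 = 42% to (50 + 75)/2 = 62.5%.

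Sensitivity: Table 1 requires an estimated life expectancy of at least 12 weeks (84/30.44 = 2.76 months). Suppose nobody dies before then and the exponential curve starts at that point:

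- Month 6, median 10: 1 − 0.5^(3.24/10) = 20%
- Month 6, median 6: 1 − 0.5^(3.24/6) = 31%
- Month 6, median 3: 1 − 0.5^(3.24/3) = 53%
- Month 3: 1 − 0.5^(0.24/10) = 2% to 1 − 0.5^(0.24/3) = 5%

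Under that assumption, deaths matter from month 6 on and not at month 3. Living non-attenders come on top; the documents give no rate for them.

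**3. Direction of the effect (illustrations; all mixes and shifts are assumed)**

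*Raw visit means.* Take equal thirds at ECOG 0, 1 and 2 with medians of 10, 6 and 3 months, and let no patient change. Month-6 survival is 0.66, 0.50 and 0.25. Mean ECOG among survivors is (0×0.66 + 1×0.50 + 2×0.25)/(0.66 + 0.50 + 0.25) = 1.00/1.41 = 0.71, against 1.00 at baseline. The raw mean improves while every within-patient change is zero.

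*Within-patient change.* Let half stay stable (median 10) and half worsen by one grade (median 3). The mean change had nobody died is +0.50. Among month-6 survivors it is 0.25/(0.66 + 0.25) = +0.27, which is less bad but still a worsening. If the first half instead improve by one grade, the full-group change is 0 and survivors show (−0.66 + 0.25)/0.91 = −0.45. If both halves have the same survival, there is no bias.

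So the direction is favourable whenever worse scores go with earlier death or non-attendance. The size depends on inputs that the documents do not give.

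**The case against.** The case for leaving this alone has several sound parts.

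- Section c.1.h only lists the measures. It specifies neither a comparison, nor raw means, nor an attenders-only analysis. This is an unspecified analysis, not a wrong choice. That stands.
- ECOG and pain appear in none of the objectives in c.1.a. The primary evaluation is CT on day 3, before planned discharge, and is untouched. Deaths are not hidden either: survival is followed, and progression-free survival is in the same secondary list. That stands and limits the importance of the point.
- The 75% figure needs an all-metastatic cohort with a 3-month median, and the life-expectancy criterion should lower early deaths. This also stands, although that criterion is an estimate and not a guarantee. Even so, 20% to 53% dead by month 6 is too many to leave without a rule.
- Counting death as the worst category is only one defensible way to define the outcome. It largely repeats survival and says less about function among the living. I agree, so it should be supportive and not the main summary.

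None of this answers the collection gap. Numbers alive and dead can be rebuilt at analysis. A missed ECOG or pain score from a patient too ill to attend cannot.

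**Conclusion.** The point holds as a gap in data collection and reporting for two secondary descriptive measures. Following the plan as written yields no ECOG or BPI score from patients who cannot attend, and no scheduled BPI from anyone. About 34% to 75% would be dead by month 6 under exponential survival at the section a.1 figures, or about 20% to 53% with no deaths before 12 weeks. Attender-only summaries will lean favourable provided that worse function or pain predicts death or non-attendance.

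A reader might go further and infer that survivors will look stable or improved after treatment. The documents do not support that. They give no baseline ECOG mix, rate of worsening, pain data or link between score and survival, and in the illustrations survivors' change can remain a worsening. A large contrast between attenders and all treated patients in the share with maintained ECOG would likewise rest on assumed inputs, and largely on counting deaths as failures. Nor can the 34% to 75% range be read as a rate the plan predicts.

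**What to change.** **Section c.1.d.** Add ECOG and BPI to the phone contact that already takes place. Schedule BPI in Table 2 at baseline and at each follow-up visit.

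**Section c.1.h.** For each scale and visit, report three counts out of all treated patients: alive and assessed, alive but missing, and dead. Present within-patient change from baseline under the label *among patients alive and assessed*, and make no before/after claim from raw visit means. As a supportive summary, the proportion of all treated patients who are alive with a score no worse than baseline can be shown alongside.

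**Cost.** A protocol wording change, one added form at existing visits, and a few more questions in an existing call. ECOG rated by phone is slightly less precise than ECOG rated in clinic, so the mode of assessment should be recorded. The reported results will look less favourable than an attender-only summary.
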